| PLANNED INTERIM ANALYSES | When the study has reached 1/3 and 2/3 goal enrollment, interim analysis for safety will be conducted by an independent data monitoring committee. Serious and severe adverse events will be monitored by the committee on an ongoing basis throughout the study. |
| STATISTICS Primary Analysis Plan & Rationale | 
Null Hypothesis: There is no difference in cumulative daily in-hospital use of opioids in subjects who receive intercostal nerve block and wound infiltration with Liposomal Bupivacaine or Standard Bupivacaine during minimally invasive lung resection.
 
Statistical Method: Student's t-test.
 
Rationale: 80 subjects will provide 80% power to detect a statistically significant effect with 2-sided alpha error set at 0.05 if the measured effect is 19% absolute reduction in cumulative daily in-hospital use of opioids.
 |

| | |
|--|---|
| | 
The mean cumulative daily in-hospital usage of opioids is 35mg morphine equivalents with standard deviation of 12mg. This was estimated by review of previously published studies and corroboration with UCSF clinical practice patterns. A 19% reduction in cumulative daily in-hospital use of opioids corresponds to 1 fewer oxycodone dose per day, which was considered clinically significant.
 |
|--|---|

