- Medical Monitor / Chairman of the DMC: [name] MD, Clinical Professor of Anesthesia at UCSF. [name] was selected as he is an expert in local amide analgesia.

Although DMC members are expected to serve for the duration of the study, in the unlikely event that a member is unable to continue participation, the reason will be documented and a replacement member will be selected by the Investigator. The new member must have comparable expertise and qualifications to the DMC member he/she is

replacing. DMC members must not have any real or perceived scientific, financial, professional, personal, proprietary, or other conflict of interest related to the conduct, outcome, or impact of the study.

Review of Safety Data

The primary charge of the DMC is to monitor the study for participant safety. The safety and related data the DMC will review includes,

- Participant recruitment, accrual, retention, and withdrawal information
- Adverse events (AEs) and serious adverse events (SAEs)
 - Tabulated by body system, intensity, seriousness, duration, treatment given, and the relationship to the study drug and study procedure
 - Comparison of events that occur between treatment arms
 - Individual events of particular concern

In particular, the following are adverse events of special interest pertinent to Liposomal Bupivacaine and Standard Bupivacaine:

- Nausea, emesis, and/or constipation and are expected to occur in >10% of subjects.
- Less common adverse events include dizziness, altered mental status, and hypersensitivity reactions with urticaria and/or pruritis.
- Very rare, but serious adverse events include neurologic toxicity with seizures and apnea, cardiac toxicity with atrioventricular nodal conduction abnormalities and cardiac arrest, and hypersensitivity reaction with anaphylaxis.

SAEs must be reported by the Investigator to the DMC Chair.

Review of Other Data

- Effectiveness

The DMC monitors effectiveness outcomes to determine relative risk/benefit, futility, or for early termination due to overwhelming effectiveness.

- Study Conduct

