15.3 Analysis of Primary Endpoint

Null Hypothesis: There is no difference in cumulative in-hospital use of opioids in subjects who receive intercostal nerve block and wound infiltration Liposomal Bupivacaine or Standard Bupivacaine during minimally invasive lung resection.

Student's t-test will be used to assess the means of the cumulative total of in-hospital oral morphine equivalents. It is presumed that the data will be normally distributed. If this assumption is not met, transformation or nonparametric tests (Mann-Whitney U test) will be used. Moreover, as there are only 40 subjects per group, it is possible that we do not achieve effective randomization. If this occurs, we will utilize linear regression adjusting for age, sex, race, comorbidity, diagnosis, and procedure performed. A power of 0.8 and 2-sided alpha error set at 0.05 will be used to assess for statistical significance.

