15.5 Interim Analysis

There will be interim reviews conducted by the DMC for the purpose of monitoring study conduct and assessing patient safety at 1/3 and 2/3 goal enrollment. Blinding will be maintained. An O'Brien-Fleming alpha spending function with symmetric stopping boundaries for benefit and harm will be utilized. If the stopping boundaries have been reached (absolute value of z-value >3), the data will be unblinded for review and the trial will be terminated. Finally, there also will be consideration of terminating trial if there is consensus of futility.

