15.6 Sample Size and Randomization

80 Subjects will be randomized to 1:1 to Liposomal Bupivacaine or Standard Bupivacaine by varying block size (4-8). 80 subjects will provide 80% power to detect a statistically significant effect with 2-sided alpha error set at 0.05 if the measured effect is 19% absolute reduction in cumulative daily in-hospital use of opioids.

The mean daily in-hospital usage of opioids is 35mg morphine equivalents with standard deviation of 12mg. This was estimated by review of previously published studies and corroboration with UCSF clinical practice patterns [12]. A 19% absolute reduction in cumulative daily in-hospital use of opioids corresponds to 1 fewer oxycodone dose per day, which was considered the minimum clinically significant effect.

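### Section 15.3 judges the primary test at two-sided 0.05 and no final critical value is given, although Section 15.5 sets benefit boundaries at two earlier looks

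*Combined protocol and SAP*

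**What the plan says.** - **Final test.** Section 15.3 names Student's t-test for the primary endpoint and closes with "A power of 0.8 and 2-sided alpha error set at 0.05 will be used to assess for statistical significance". It does not refer to Section 15.5, an adjusted level or a final boundary.
- **Interim looks.** Section 15.5 places DMC reviews at 1/3 and 2/3 of goal enrollment. It names O'Brien-Fleming and says that an "alpha spending function with symmetric stopping boundaries for benefit and harm will be utilized". The one number it prints is an absolute z-value above 3, on which the trial is unblinded and terminated. It states no total alpha and no final boundary, and does not say which endpoint the z-value tests.
- **Charter.** Section 14.1, under Review of Other Data, has the DMC monitor effectiveness outcomes for purposes that include "early termination due to overwhelming effectiveness". Its Stopping Rules repeat that ground.
- **Stated purpose of the looks.** The Synopsis says that "interim analysis for safety will be conducted by an independent data monitoring committee". Section 14 and the first sentence of 15.5 likewise speak of study conduct and patient safety.
- **Planning alpha.** Section 15.6 and the Synopsis state that "80 subjects will provide 80% power to detect a statistically significant effect with 2-sided alpha error set at 0.05".

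**The concern.** A look that can end the trial for benefit uses part of the type I error. If the last test is then run at an unadjusted two-sided 0.05, the total exceeds 0.05. Section 15.3 is the rule an analyst would follow for the primary result, and it gives 0.05 without qualification. Under the boundary that 15.5 prints, a final p-value between 0.0483 and 0.050 would be declared significant when it should not be. Under O'Brien-Fleming spending boundaries the affected range starts at about 0.046. A borderline primary result would then be open to dispute, and nothing in the plan would settle it.

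**Working it through.** **Inputs.** Looks at information t = 1/3, 2/3 and 1 (15.5); two-sided 0.05, so a final cut of 1.96 (15.3); |z|>3 at both looks (15.5); 40 per arm (80 subjects, 1:1, 15.6); "The mean daily in-hospital usage of opioids is 35mg morphine equivalents with standard deviation of 12mg"; and an effect of "19% absolute reduction in cumulative daily in-hospital use of opioids", that is 0.19 × 35 = 6.65 mg.

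**Step 1: the plan's own power figure.** The standard error is 12 × √(2/40) = 2.683 mg, and 6.65 / 2.683 = 2.478. Fixed-sample power at two-sided 0.05 is Φ(2.478 − 1.960) = 0.698 (0.687 by the noncentral t), not 0.80. That shortfall is a separate and larger matter. Here 6.65 mg serves only as the reference point for the cost of a corrected boundary.

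**Step 2: the null model.** Under no difference the three z-statistics are jointly normal with correlation √(t_j/t_k). Overall alpha = P(|Z1|>c1 or |Z2|>c2 or |Z3|>c3), found by recursive numerical integration.

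**Step 3: the printed boundary.** With c1 = c2 = 3, the first look uses 0.0027 and the two together use 0.0049. Adding a final cut of 1.96 brings the total to 0.0517 (0.0519 in a simulation of 4 million trials). Solving for the final cut that restores 0.05 gives 1.975.

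**Step 4: O'Brien-Fleming boundaries.** The usual O'Brien-Fleming-type spending function with 0.025 in each tail is α(t) = 4[1 − Φ(2.2414/√t)]. Cumulative spending is 0.0002, 0.0121 and 0.05, and the boundaries are 3.710, 2.511 and 1.993. The classical O'Brien-Fleming design gives 3.471, 2.454 and 2.004.

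**Step 5: side by side.** Power is for 6.65 mg with all three looks included.

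| Interim boundaries | Overall alpha, final 1.96 | Final cut for 0.05 | Nominal final p | Power, final 1.96 | Power, corrected cut |
|---|---|---|---|---|---|
| 3, 3 (printed in 15.5) | 0.0517 | 1.975 | 0.0483 | 0.700 | 0.695 |
| 3.710, 2.511 (spending) | 0.0535 | 1.993 | 0.0463 | 0.703 | 0.692 |
| 3.471, 2.454 (classical) | 0.0546 | 2.004 | 0.0451 | 0.704 | 0.690 |

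**Step 6: the boundaries must be set together.** A constant 3 is not an O'Brien-Fleming boundary at these looks, so 15.5 names one rule and prints another. Joining the printed 3, 3 to the spending function's final 1.993 gives an overall alpha of 0.048, not 0.05.

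**The case against.** A reader might infer that the trial's type I error certainly exceeds 0.05. The documents do not go that far. A spending function divides a fixed total, 0.05 is the only alpha in the plan, and 15.3 gives it in the same sentence as the power, as one would give a design parameter. If 0.05 is the total and the final cut follows from the spending function, the overall error is 0.05. This reading is tenable. But 15.3 does not state it, 15.4 uses near-identical wording for the secondary endpoints where 0.05 can only be a per-test level, and the final cut cannot be derived from 15.5 because its method and its number disagree.

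A reader might also infer that 15.6 and the Synopsis set the final test level. They do not. Each gives a planning alpha in a power statement, where quoting the overall alpha is normal. Only 15.3 bears on the test.

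A third objection is that the looks may concern safety alone, since the Synopsis, Section 14 and the opening of 15.5 say so and no endpoint is attached to the z-value. That stands as an ambiguity. Against it, 15.5 has a boundary for benefit and the charter twice allows stopping for effectiveness.

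Finally, Section 15 promises a detailed SAP that could supply the boundary. It is due only before analysis of the final data, so nothing requires it before the interim looks.

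**Conclusion.** The point holds in a limited form. Sections 15.3 and 15.5 are not reconciled and the final critical value is missing. If 15.3 is followed literally and the looks test the primary endpoint, the excess over 0.05 is 0.17 percentage points under the only boundary printed, and 0.35 to 0.46 points under O'Brien-Fleming interim boundaries. The final cut of 1.96 is too lenient under all three. The text does not prove that the error rate is inflated.

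The figures assume information fractions of exactly 1/3 and 2/3, normal-theory statistics, and no credit for futility stopping, for which 15.5 gives no numerical rule. The size is modest. The correction should still be made before the first look, because a threshold chosen after comparative data have been seen is harder to defend.

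**What to change.** 1. In 15.3, state that 0.05 is the overall two-sided alpha across the two looks and the final analysis, and refer to 15.5 for the final boundary. The 0.05 in 15.6 and the Synopsis can stay if labelled overall.
2. In 15.5, name the endpoint behind the z-value and print one consistent set of three boundaries: either 3, 3, 1.975 (final p<0.0483), dropping the O'Brien-Fleming label, or O'Brien-Fleming spending 3.710, 2.511, 1.993 (final p below about 0.0463), dropping the constant 3. Changing the final level alone is not enough, as Step 6 shows.
3. Alternatively, make the looks safety-only throughout, as the Synopsis describes them, by deleting the benefit boundary in 15.5 and the effectiveness stop in the charter. The final test at 0.05 then stands.

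The cost is wording. At 6.65 mg, power falls from 0.700 to 0.695 with the first set (about 0.5 points) and from 0.703 to 0.692 with the second (about 1.1 points). No extra subjects are needed for this change.

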15.4 Analysis of Secondary Endpoints

- Cumulative Daily In-Hospital Pain Score (0-10)
- Mean Time to First Opioid Use (hours)
- Mean Time to Ambulation (hours)
- Pulmonary Complications: Pneumonia and Atelectasis requiring Bronchoscopy (y/n)
- Liposomal Bupivacaine and Stand Bupivacaine Adverse Events (y/n):
 - Gastrointestinal- nausea, emesis, constipation
 - Hypersensitivity- pruritis, urticaria, anaphylaxis
 - Cardiac- atrioventricular heart block, cardiac arrest
 - Neurologic- dizziness, altered mental status, seizure
 - Miscellaneous

Safety and tolerability data will be summarized by treatment group. Adverse event rates will be coded by body system and will include the number of patients for whom the event occurred, the rate of occurrence, and the severity and relationship to study drug.

- Length of Stay (days)
- Total Opioid Prescription at Discharge (morphine equivalents in mg)
- Total Opioid Use as Outpatient (morphine equivalents in mg)
- Direct Costs of hospital encounter (dollars)
- Quality of life – Short-Form-8 Health Survey (Optum Health)

Student's t-test, Pearson's chi-squared test, and Kaplan-Meier survival estimate will be used. A 2-sided alpha error set at 0.05 will be used to assess for statistical significance.

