3.2 Secondary Objectives

The secondary objective is to assess if analgesia from the aforementioned interventions improve perioperative outcomes with reduction in pulmonary complications, length of stay, and direct hospital costs as well as improvement in quality of life.

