5.2 Secondary Efficacy Endpoints

- Cumulative Daily In-Hospital Pain Score: 0 (no pain) – 10 (most pain)

Pain Scores are a measure of the subject's postoperative pain that are recorded every four hours by the nursing staff. They are limited by the subject's perception of pain, concomitant pain medication use, and correlation with an abstract scaling system.

- Mean Time to First Opioid Use (hours)

Time to first opioid use is a surrogate marker of postoperative pain. It is limited by variations in anesthesiologist intraoperative analgesia techniques.

- Mean Time to Ambulation (hours)

Time to ambulation is a downstream marker of postoperative pain control. Ambulation is limited by subject motivation and/or physical disability.

- Pulmonary Complications: Pneumonia and Atelectasis requiring Bronchoscopy (y/n)

Pulmonary complications are a downstream marker of postoperative pain control as subjects with chest wall postoperative pain commonly splint with respiration. Splinting is associated with atelectasis and pneumonia.

- Liposomal Bupivacaine and Stand Bupivacaine Adverse Events (y/n):

- Gastrointestinal- nausea, emesis, constipation
- Hypersensitivity- pruritis, urticaria, anaphylaxis
- Cardiac- atrioventricular heart block, cardiac arrest

- Neurologic- dizziness, altered mental status, seizure
- Miscellaneous

To assess if there are differences in the complications between the study groups.

- Length of Stay (days)

Length of stay in the hospital can be used as downstream marker of overall postoperative course. It is limited by attending practice patterns.

- Total Opioid Prescription at Discharge (morphine equivalents in mg)

To assess if there are differences in the amount of opioid prescribed at discharge.

- Total Opioid Use as Outpatient (morphine equivalents in mg)

To assess if there are differences in the amount of opioid used after discharge.

- Direct Costs of Hospital Encounter (dollars)

The interventions in the study add costs over standard of care. It is important to evaluate the burden on the health care system in addition to subject outcomes.

- Quality of Life: Short-Form-8 Health Survey (Rand Health)

A change in quality of life before and after surgery will be assessed. This survey is limited by subject adherence to completion.

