15 STATISTICAL METHODS AND CONSIDERATIONS

Prior to the analysis of the final study data, a detailed Statistical Analysis Plan (SAP) will be written describing all analyses that will be performed. The SAP will contain any modifications to the analysis plan described below.

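### Section 15.4 judges ten secondary endpoints at an unadjusted two-sided 0.05, with no testing order, no link to the primary result and no exploratory label

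*Combined protocol and SAP*

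**What the plan says.** Section 15.4 lists ten secondary endpoints: pain score, time to first opioid, time to ambulation, pulmonary complications, adverse events, length of stay, opioid prescribed at discharge, opioid used as an outpatient, direct hospital cost, and SF-8 quality of life. The adverse-event endpoint has five sub-categories: gastrointestinal, hypersensitivity, cardiac, neurologic and miscellaneous.

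On methods, it names Student's t-test and continues with Pearson's "chi-squared test, and Kaplan-Meier survival estimate will be used". It does not assign a method to each endpoint. The decision rule follows: "A 2-sided alpha error set at 0.05 will be used to assess for statistical significance". Section 15.3 uses the same two-sided 0.05 for the primary endpoint.

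On adverse events, 15.4 says "Safety and tolerability data will be summarized by treatment group". Section 5.2 gives the purpose of that endpoint as "To assess if there are differences in the complications between the study groups".

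Section 3.2 takes up four of the ten, asking whether better analgesia leads to "reduction in pulmonary complications, length of stay, and direct hospital costs as well as improvement in quality of life".

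Section 15 promises a later, detailed SAP: "The SAP will contain any modifications to the analysis plan described below". It does not say that the SAP will address multiplicity. The O'Brien-Fleming function in 15.5 governs interim stopping, not the number of endpoints.

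**The concern.** Many trials leave secondary endpoints unadjusted, but then call them exploratory or make no significance claims. This plan does neither. It states a significance rule and applies it to the list as a whole, without regard to how many endpoints there are or whether the primary result is significant.

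Followed exactly, the rule allows a single secondary result with p < 0.05 to be reported as statistically significant when the primary is null and nothing truly differs. Some of these endpoints would carry weight. Section 2 puts the direct cost of the liposomal product at 100 times that of standard bupivacaine and raises possible savings elsewhere as the offset. A chance finding on cost or pulmonary complications would bear directly on that argument.

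**Working it through.** The documents give no familywise error rate for the secondary endpoints, so there is no plan figure to reproduce. The check asks what the stated rule implies.

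**Inputs from the documents.** Per-test level 0.05, two-sided (15.4). Ten endpoints (15.4 and 5.2 agree). Forty subjects per arm (80 subjects at 1:1, 15.6). If the five adverse-event categories were tested separately, the count would be 9 + 5 = 14.

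**Step 1: independent tests, every null true.** P(at least one p < 0.05) = 1 − 0.95^k.

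| Tests counted | k | Result |
|---|---|---|
| All ten listed | 10 | 1 − 0.95^10 = 40.1% |
| One drops out (adverse events only summarised, or discharge prescription contributes nothing) | 9 | 1 − 0.95^9 = 37.0% |
| Both drop out | 8 | 1 − 0.95^8 = 33.7% |
| Five adverse-event categories tested separately | 14 | 1 − 0.95^14 = 51.2% |

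The discharge prescription is considered because Section 7.1 sends all subjects home with 20 oxycodone pills, so it may vary little between arms.

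**Step 2: correlated tests.** The documents give no correlations, so these are assumed: a common correlation between normal test statistics, two-sided tests, 400,000 simulated draws.

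| Assumed correlation | 10 tests | 14 tests |
|---|---|---|
| 0.2 | 38% | 48% |
| 0.3 | 35% | 44% |
| 0.5 | 29% | 35% |
| 0.7 | 21% | 25% |

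**Step 3: rare binary outcomes.** The exact size of Pearson's chi-squared test at 40 per arm, nominal 0.05, depends on the event rate. The rates here are assumptions.

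| Assumed rate per arm | Size |
|---|---|
| 1% | 0.1% |
| 2% | 0.7% |
| 5% | 4.3% |
| 10% | 5.9% |

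If pulmonary complications occur at 1–2%, the independent ten-test figure falls from 40% to about 37%. If the cardiac, hypersensitivity and pulmonary outcomes all occur at 1–2%, the independent fourteen-test figure falls from 51% to 43–44%.

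**Step 4: expected number of false positives.** If every test has true size 0.05, this is 10 × 0.05 = 0.5 for ten tests and 8 × 0.05 = 0.40 for eight, whatever the correlation. Step 3 shows that the condition fails for rare events, so 0.5 is in effect an upper figure for ten tests. The slight excess at a 10% event rate adds less than 0.01 per endpoint (0.059 − 0.050).

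**The case against.** The strongest reply is that this is largely convention. There is one prespecified primary endpoint, and the rest are labelled secondary. Section 5.2 states limitations for several of them, and nothing says that a secondary result can rescue a null primary. A detailed SAP is still to come. Independence is also implausible: pain score, time to first opioid, ambulation, length of stay and outpatient opioid use all reflect pain control to some degree, and cost follows stay.

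Much of this stands, and it limits what can be said.

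- A reader might infer that a spurious secondary finding is nearly a coin toss. That needs fourteen independent tests. Section 15.4 describes a summary of safety data. Section 5.2 makes a between-group comparison possible, but neither section says that the five categories will be tested one by one.
- A reader might infer 0.5 to 0.7 expected false positives regardless of correlation. That holds only if every test has size 0.05, which fails for rare binary outcomes and is doubtful for a standardised discharge prescription.
- A reader might take Section 3.2 as asserting benefit. Its wording is an aim to assess whether outcomes improve, and the synopsis asks more neutrally about changes. These are questions, not claims.
- A reader might infer that every endpoint has a named significance test. The Kaplan-Meier method is an estimate, and no log-rank test is named.

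What does not stand is the appeal to convention or to the later SAP as a cure. The convention depends on an exploratory label or restraint in claims, and the plan has neither. The SAP is the natural place for the repair, but nothing commits it to one, so the 0.05 rule remains the default.

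**Conclusion.** The concern holds in limited form. Section 15.4 sets a significance rule for ten secondary endpoints with no multiplicity control, and no other section supplies any. If all nulls are true, the chance of at least one false significant result is up to about 40% for ten independent tests. It is 34–37% with one or two fewer contributing tests, and about 21–38% for ten tests at assumed common correlations of 0.7 to 0.2. The lowest of these is still about four times 5%.

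These figures rest on the count of ten, on no true effect on any endpoint, and, for the last range, on assumed correlations. The count could also be exceeded, because the plan does not say whether the pain score is tested by day or whether SF-8 yields more than one score.

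The primary analysis is unaffected. This is a cheap improvement, not a flaw that threatens the trial's main conclusion.

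**What to change.** Replace the last sentence of 15.4, and carry the same text into the SAP before unblinding:

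> Secondary efficacy endpoints are exploratory; they will be reported as estimates with 95% confidence intervals not adjusted for multiplicity, and no claim of statistical significance will be made. Adverse events will be summarised by treatment group, with between-group differences and 95% confidence intervals, and potential harm signals will be reported without multiplicity adjustment.

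The separate sentence for adverse events keeps the restriction on claims from muting a harm signal. Unadjusted intervals do not remove multiplicity, since a reader can still see which exclude zero. That is why the wording says they are unadjusted.

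If formal secondary claims are wanted, name the endpoints in advance (for example the four in 3.2), test them only if the primary is significant, and apply Holm. With four endpoints the first threshold is 0.05/4 = 0.0125. Those four leave out the pain score, the most direct measure of pain, so the choice should be deliberate. Adding it would make the first threshold 0.05/5 = 0.01.

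The change needs no extra subjects, data or procedures. Its cost is fewer formal secondary claims.
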